4.4 Metrics and Variables

The primary outcome of interest is COVID-related hospitalization rate in study participants and matched controls. We list all potential covariates in two phases. Phase I covers historical data and Phase II includes post COVID-19 diagnosis information. Phase I historical data will be collected for both study participants and matched controls. Phase II post-COVID 19 diagnosis data has two parts: data elements to be collected for both study participants and matched controls (Phase II.A), and data elements to be collected for only study participants (Phase II.B).

Phase I - Historical data: Study participants and matched controls:

1. COVID-19-related information:

- Symptomatic or asymptomatic during COVID-19 test
- Number of COVID-19 cases per 10,000 people in the county of residence during COVID-19 test (if available)
- Number of COVID-19 deaths per 10,000 people in the county of residence during COVID-19 test (if available)

2. Demographic:

- Age as of 2020
- ZIP code of residence (may or may not be used for identifying matched controls)
- Urbanization of residence in a zip code level (urban, suburban, rural)
- Region/State of residence
- Race
- Gender
- Flag determining whether a patient resides in a nursing facility (or has been staying in a nursing facility currently) – determining patient does not live at home

3. Insurance:

- Line of business (should be mostly Medicare)
- Dual-eligibility status
- Continuous member enrollment in 2019
- Continuous member enrollment in 2020

3. Comorbidities in 2019:

- History of chronic kidney disease
- History of diabetes
- History of immunosuppressive disease
- History of cardiovascular disease
- History of hypertension
- History of chronic obstructive pulmonary disease/other chronic respiratory disease

- Elixhauser score for readmission
- Historical flag for all other associated comorbidities used in computing Elixhauser score (i.e., 29 categories like kidney disease, cancer etc.)

4. Immunosuppressive treatment

- History of receiving immunosuppressive treatment (6 months prior to date of COVID diagnosis)

Phase II.A: Post COVID-19 diagnosis data: Study participants and Matched controls

- Date of COVID-19 diagnosis test
- Type of COVID-19 diagnosis test (e.g., PCR, Antigen)
- Hospital admission date (if patient is hospitalized)
- Type of hospital admission (measuring level of trauma) (if available)
 - Through ER (if any)
 - With ICU transfer (if any)
 - With ventilation (if any)

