4.4.2 Patient Groups

Before analysis there are two study populations – study participants and the pool of potential controls. For study participants, we plan to enroll aged 65 and older, who are deemed high risk per the emergency use authorization, if contracting COVID-19. For the pool of potential controls, we plan to utilize UHC members who have Optum EMR data to confirm presence of symptoms during COVID test as well as having continuous enrollment to access to their claims and prospective hospitalization and death data. If applicable, non-UHC members or UHC members who did not seek care at OptumCare facilities may be used as members of the control population based on EMR review and matching to enrolled participants.

During analysis (i.e., after matching), there will be two study populations – study participants after matching and matched controls. Note that the size of study participants after matching may be smaller than the size of original study participants if a matched control can't be identified.

The targeted number of enrolled participants for tracking for symptoms is 500,000, and the targeted number of study participants who are COVID-19 positive and consent to receive Bamlanivimab (LY3819253) is 7,500. Figure 2 illustrates the process to identify study participants. Regarding controls, we set the case:control ratio at 1:1 and plan to identify 7,500 matched controls which is the same as number targeted for study participants.

Given the current enrollment speed (as of March 9, 2021) and the decreasing COVID-19 hospitalization rate across the US, we may not achieve the target number of study participants, 7,500. However, according to the power analysis in Section 4.3, it is sufficient to have 1,000 study participants with another 1,000 matched controls to detect a 33% decrease in the hospitalization rate (i.e., from 15% to 10%) with power 0.8 and level 0.05.

Commented [JAT7]: Remove as treatment is allowed in this situation per the EUA.

Commented [JAT8]: Remove prior vaccination from exclusion criteria as this is not required per the EUA.

Commented [WWY9]: Should we replace continuous member enrollment?

Commented [WWY10]: Given current enrollment speed, it will be helpful to show what is the minimal sample size for Bam treated group required for the primary objective analysis.

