4.7 Variables/Measures

The primary outcome of interest is COVID-related hospitalization rate in study participants and matched controls. We list all potential covariates in two phases. Phase I covers historical data and Phase II includes post COVID-19 diagnosis information. Phase I historical data will be

collected for both study participants and matched controls. Phase II post-COVID 19 diagnosis data has two parts: data elements to be collected for both study participants and matched controls (Phase II.A), and data elements to be collected for only study participants (Phase II.B).

Phase I - Historical data: Study participants and matched controls:

1. COVID-19-related information:

Variable	Data source for study participants	Data source for matched controls
Date of COVID-19 diagnosis test	ProtectWell	Optum EMR or CDSM
Type of COVID-19 diagnosis test*		
Symptomatic flag during COVID-19 test	ProtectWell (all study participants are symptomatic)	Optum EMR
Previous COVID diagnosis flag	CDSM	Optum EMR or CDSM
Previous receipt of Bamlanivimab	UHC claims	Optum EMR or UHC Claims

*: Please see Table A1 in Appendix 1 for LOINC codes of the PCR and antigen COVID-19 tests.

Commented [WWY15]: This variable won't be used for analysis.

Commented [JAT16R15]: Not necessarily. We'll use it to approximate date of symptoms onset and identify matched controls who got COVID-19 around the same time. Please see the comment below for more details.

Commented [WWY17]: Would also include COVID-19 symptoms, and a timing variable: duration since symptom onset to index date

Commented [JAT18R17]: We will include these data fields if available. Regarding date of symptoms onset, it's approximated to be 2 days prior to date of COVID-19 diagnosis (1 day for overnight shipping of COVID-19 test kit and the other day for PCR test).

2. Demographic:

Variable	Data source for study participants	Data source for matched controls
Age as of 2021*		
ZIP code of residence (may or may not be used for identifying matched controls)		
Urbanization of residence in a zip code level (urban, suburban, rural)		
Region/State of residence		
Race		
Gender		
Flag determining whether a patient resides in a nursing facility – determining a patient does not live at home		

*: Age = 2021 – birth year.

Commented [WWY19]: As obesity is a high risk factor, suggest to include BMI as a covariate in PS matching

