5.1 General Considerations

Statistical analysis of this study will be the responsibility of the sponsor or its designee. All tables, figures, and listings will be created using the data described in Table 1 and Section 4.7 (unless otherwise noted), including data during study participation. While not reflected in a table, figure, or listing, any data collected after study participation (e.g., in the Lilly Safety System or collected through queries to the investigator) may be discussed in a clinical study report (CSR) or integrated summary document when deemed relevant. Unless otherwise noted, displays will include columns for study participants and controls will be displayed.

Not all displays described in this statistical analysis plan (SAP) will necessarily be included in the CSR. Not all displays will necessarily be created as a “static” display. Some may be incorporated into interactive display tools instead of, or in addition to, a static display. Any display described in this SAP and not provided would be available upon request.

Treatment differences will be evaluated based on a two-sided significance level of 0.05 for all efficacy analyses. Ninety-five percent confidence intervals for the estimated event rate, odds ratio/hazard ratio will be provided. While we describe many methods addressing different uncertainties, we may not need to perform all analyses mentioned in the draft. Additional exploratory analyses of the data will be conducted as deemed appropriate. All statistical analyses will be performed using R 3.6 (or a higher version).

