5.1.1 Populations for Analyses

We define the analysis populations in Table 3 along with the analysis we will conduct. All patients meet the study eligibility criteria. Note that all populations for analyses are UHC members, and the following proposed analytical methods are for UHC members. We may see non-UHC members satisfying the study eligibility criteria, but we cannot obtain or have very limited information of their comorbidities, demographic (e.g., area of residence, socioeconomic index), and if having immunosuppressive treatment prior to COVID-19 diagnosis.

Table 3. Population for analyses

Population	Data for analysis	Definition/Data
Study participants	Disposition analysis and safety	Study participants who sign informed consent and receive Bamlanivimab in single infusion of 700 mg.
Pool of potential controls	Formation of the control group Pre-matching identification of risk factors Estimation of prognostic scores	Patients who meet the study eligibility criteria but did not receive Bamlanivimab.

Commented [WWY23]: Would suggest to revise to include general results reporting, definition of the analysis populations, analysis methods, definition of baseline Refer to attached sample SAP

Overall population	Descriptive analyses Propensity score matching	Consists of study participants and pool of potential controls.
Propensity score matched population	Efficacy and descriptive analyses	Subset of the overall population consisting of study participants and matched controls after propensity matching.
Double score (propensity score and prognostic score) matched population	Sensitivity analyses	Subset of the overall population consisting of study participants and matched controls after double matching.

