Table A8. Standardized difference in mean and variance ratio of the propensity score and all matching covariates before propensity score matching

Commented [XM58]: Would report both results before and after match

Variable	Standardized difference in mean	Variance ratio
Propensity score		
Age (continuous or categorical):		
65-		
65 – 69		
70 – 74		
75 – 79		
80+*		
*: We can separate 80+ into finer groups as needed.		
Gender		
Race:		
White		
Black		

LY3819253

CONFIDENTIAL

[Protocol number: UHG (J2X-NS-I002)] SAP [\[v.3\]](#)

Asian	
Hispanic	
Other	
Urbanization of residence:	
Urban	
Suburban	
Rural	
Socioeconomic index	
Dual status	
With Medicaid	
Elixhauser comorbidity score	
Elixhauser conditions [*]	
[*] : There are 29 conditions in total as shown in Table A1.	
Immunosuppressive treatment 6 months prior to date of COVID diagnosis	

Dataset: dataset location (data table name with the corresponding database in Google BigQuery)

Program: program location/program name.R

Output: output location/output name.csv or .xlsx

Repeat Table A8:

Table A8.2

Standardized difference in means and variance ratio of the propensity score and all matching covariates after propensity score matching

Propensity score matched population

Programming notes:

Replace “before propensity score matching” with “after propensity score matching” in the table title.

LY3819253

CONFIDENTIAL

[Protocol number: UHG (J2X-NS-I002) SAP [v.3]

Table A9. Unadjusted and adjusted measures of COVID-19 hospitalization risk in study participants and matched controls.

Outcome	Results (e.g., 95% CI and p-value)
Rate of COVID-19 hospitalization w/o considering censoring on Day 28 (i.e. binary endpoint) among study participants vs matched controls	
Adjusted odds ratio w/o considering censoring on Day 28 (i.e. binary endpoint) among study participants vs matched controls	
Adjusted hazard ratio with considering censoring on Day 28 among study participants vs matched controls	

Commented [XM59]: Would include 95% CI and p value.

Commented [XM60]: Not sure what this mean?

Commented [JAT61R60]: This means a binary response. If we don't observe a covid-19 hospitalization for a patient within 28 days after his/her treatment, we define this response as 0, instead of censoring on Day 28.

Dataset: dataset location (data table name with the corresponding database in Google BigQuery)

Program: program location/program name.R

Output: output location/output name.csv or .xlsx

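### The SAP's stated intent to use contemporaneous controls is not carried into the control pool, the matching rule, the covariate adjustment or the balance tables

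*SAP*

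**What the plan says.** - **Intent.** SAP 4.7 lists the date of the diagnostic test among its Phase I variables, with a source for each group. Protocol 4.4 had placed that date among post-diagnosis data (Phase II.A). In the margin of SAP 4.7, a comment says a variable will not be used in the analysis. The reply disagrees: it will be used to approximate symptom onset and to "identify matched controls who got COVID-19 around the same time".
- **Control pool.** SAP 5.1.1, Table 3: "Patients who meet the study eligibility criteria but did not receive Bamlanivimab". No date window is given.
- **Matching rule.** SAP 5.8.1.2 fits the propensity model on the risk factors chosen in 5.8.1.1 and uses nearest-neighbour 1:1 matching within an empirically set caliper. It names no test-date stratum, date caliper or local incidence. SAP 5.8.1.1 offers state or county as an example of a candidate risk factor.
- **Adjustment.** SAP 5.2 names treatment, age, gender, the qualifying risk factors and any further risk factors found by regression. Calendar time is not named.
- **Balance check.** Table A8 is titled as covering "all matching covariates before propensity score matching", and A8.2 repeats it after matching. The rows are propensity score, age, gender, race, urbanization, socioeconomic index, dual status, Elixhauser score and conditions, and immunosuppressive treatment. A11 has the same covariate rows. Neither has test date, region or incidence.
- **Epidemic level.** Protocol 4.4 lists county case and death rates per 10,000 at the time of the test, if available. SAP 4.7 lists neither, and SAP 5.14 gives changes to protocol-planned analyses as not applicable.
- **Trend.** SAP 4.4.2 refers to "the decreasing COVID-19 hospitalization rate across the US" when explaining why 7,500 participants may not be reached.

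**The concern.** The primary comparison is not randomised, so its validity rests on the match. A propensity score balances only what it contains. If test date is not in the model and not a matching stratum, participants from one part of the epidemic can be paired with controls from another, where variants, care and admission thresholds may differ. The synthetic treatment date in SAP 4.5 does not help: it aligns days since symptom onset, not calendar dates.

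The planned safeguards share the gap. The repeat-until-balanced step works on the listed covariates, so an imbalance in time would pass unseen. The first-listed test is an unadjusted McNemar test. Double-score matching (5.8.2) draws on the same undated pool, and the E-value is optional. SAP 5.8.2 itself names viral variants as an unmeasured confounder, yet test date, a measured proxy for them, is already collected.

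**Working it through.** **Inputs.** SAP 4.4.2 calls 1,000 per group enough "to detect a 33% decrease in the hospitalization rate (i.e., from 15% to 10%) with power 0.8 and level 0.05"; the full target is 7,500 per group. From SAP 5.1: "Treatment differences will be evaluated based on a two-sided significance level of 0.05 for all efficacy analyses". The documents give no size for any time trend and no age for the controls, so both are assumptions below.

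**Step 1: reproduce the plan's figure.** With p1 = 0.15, p2 = 0.10 and mean p̄ = 0.125:

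n per group = [1.960·√(2·0.125·0.875) + 0.842·√(0.15·0.85 + 0.10·0.90)]² / 0.05² = 686 (726 with continuity correction).

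Power at 1,000 per group is 0.92 (0.91 corrected). The SAP's claim that 1,000 per group is enough for 80% power therefore holds, with room to spare. The continuity-corrected formula at 90% power also returns SAP Table 2, for example 940 in total for the 35% reduction.

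**Step 2: same test, no drug effect.** Let pc be the control rate and pt the participants' rate, which differ only because of calendar time:

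P(false benefit) = Φ{ [(pc − pt) − 1.96·√(2p̄(1−p̄)/n)] / √([pc(1−pc) + pt(1−pt)]/n) }

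Worked case: pc = 0.15, pt = 0.135, n = 1,000. This gives (0.015 − 1.96·0.015633)/0.015629 = −1.00, and Φ(−1.00) = 0.16.

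**Step 3: vary the trend, all controls older (pc = 15%).**

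| Relative fall | pt | Apparent RR | 1,000 per group | 7,500 per group |
|---|---|---|---|---|
| 5% | 14.25% | 0.95 | 6.9% | 25% |
| 10% | 13.5% | 0.90 | 16% | 75% |
| 20% | 12.0% | 0.80 | 50% | >99.9% |
| 33% | 10.0% | 0.67 | 92% | >99.9% |

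**Step 4: vary the share f of older controls.** Early risk 15%, late risk 10%, pt = 10%, pc = 0.10 + 0.05f.

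| f | pc | Apparent RR | 1,000 per group | 7,500 per group |
|---|---|---|---|---|
| 0 | 10% | 1.00 | 2.5% | 2.5% |
| 25% | 11.25% | 0.89 | 15% | 70% |
| 50% | 12.5% | 0.80 | 42% | 99.8% |
| 100% | 15% | 0.67 | 92% | >99.9% |

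The row f = 0 is the position once controls are contemporaneous. More patients make a given bias more likely to reach significance, not less.

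**Step 5: checks.** A McNemar approximation with 1,000 pairs and f = 50% gives 42% to 51% for within-pair correlations of 0 to 0.2, so the choice of test does not drive the result. If the rates are swapped (controls 10%, participants 15%, no drug effect), the chance of a significant apparent harm at 1,000 per group is 92%.

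**The case against.** A reader might infer that the SAP ignores calendar time, that controls will come from any earlier period, and that the result must favour the drug. The documents do not support that.

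- *Time and place are not ignored.* Test date is a listed potential covariate in the body of SAP 4.7, and the margin reply states the purpose. State or county is a candidate matching covariate. Table A5, a companion mock table, says its variables may change, so a missing row in A8 is not proof of exclusion. All this stands. But a candidate need not be selected: 5.8.1.1 looks for covariates consistent across three iterations, one of them in participants only, whose test dates may span too short a period to show an association.
- *Controls may not be very old.* They must meet the same eligibility criteria, including being where the drug is available, and 4.7 lists 2021 enrolment for both groups. This may limit their age. The availability criterion can also be read as purely geographic, and neither item aligns dates within pairs.
- *Direction is not established.* The sentence on falling rates concerns accrual and may describe a population rate. Only a change in risk per infected patient biases this endpoint directly. This stands, so the direction must be stated conditionally.
- *The size is illustrative.* The 15% and 10% are the SAP's design rates for control and treated patients, reused here as early and late background risks. The match between the last row of each table and the design effect is therefore built in. The smaller falls in Step 3 have much smaller effects at 1,000 per group.
- *County rates were conditional.* The protocol called them potential covariates, if available. Leaving them out is a weak basis for alleging an unrecorded change, but it does remove the one planned measure of local epidemic level.

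**Conclusion.** The point holds as a gap between stated intent and operative specification. The sponsor means to use controls infected at about the same time, but no rule in Table 3, 5.8.1.2 or 5.2 makes that happen, and Tables A8 and A11 would not reveal a failure. An analyst following the SAP exactly could use non-contemporaneous controls.

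The consequence is conditional. Falling per-patient risk with older controls biases towards the drug; rising risk with older controls, or falling risk with later controls, biases against it. On the stated assumptions (no drug effect, 1,000 per group, baseline 15%, all controls older), the chance of a significant false benefit runs from about 7% for a 5% relative fall to 92% for a 33% fall, against a nominal 2.5%. With early and late risks of 15% and 10%, it is 15% if a quarter of controls are older and 42% if half are. The documents establish neither the trend nor the age of the controls, so these figures show sensitivity and do not predict the bias. The gap should be closed before outcome data are accessed.

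**What to change.** 1. **Table 3:** limit the pool to positive tests within the participants' range of test dates.
2. **Section 5.8.1.2:** add an exact stratum or caliper on test date, for example 7 to 14 days, with a pre-stated rule for widening it if too many participants go unmatched. Include region or state.
3. **Propensity model:** include county case and death rates at the test date where available, and restore them to the variable list in 4.7.
4. **Tables A8 and A11:** add rows for test date, region and county rates, before and after matching.
5. **Section 5.14:** record the change.

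The cost is SAP wording and programming on a date already collected; the stated sample sizes do not change. The downside is that some participants may lose a match. How many cannot be estimated, because the documents give no control-pool size. The number should be reported in Table A7, by reason.

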5.2 Adjustment for Covariates

Unless otherwise specified, for the efficacy analysis, when logistic regression model or Cox proportional hazards model are used, the model include treatment group, age, gender, and all risk factors as part of the qualification to enter the study. Any additional variables found to be risk factors for the COVID-19 related hospitalization, per the regression model in Section 5.8, will also be included. The final list of variables will be confirmed with the study team prior to initiating the outcome analyses.

5.3 Multiple Comparisons/Multiplicity

All analyses will be conducted at the two-sided 0.05 significance level without adjustments for multiplicity.

5.4 Participant Dispositions – Study Participants Group Only

The number and percentage of study participants who complete the study or discontinue early will be tabulated by 28 days. Here, we consider that the subset of study participants for whom outcome data can be obtained through UHC claims, Optum EMR, or Optum infusion pharmacy data sources during the 28 days post-infusion time period are completing the study, whereas remaining subset of study participants for whom outcome data cannot be confirmed by any of these data sources during the 28 days post-infusion time period are discontinuing early. All patients who enter the study and discontinued from the study will be listed, and if available, the timing (from receiving study treatment) and reason of discontinuing the study will be reported.

Commented [XM24]: The number and percentage of study participants who complete the study or discontinue early will be tabulated by 28 days. Reasons for discontinuation will be summarized.

All patients who enter the study and discontinued from the study will be listed, and the timing of discontinuing (from receiving study treatment) the study will be reported. If known, a reason for their discontinuation will be given.

In addition, a graphical summary (i.e., KM plot) of time from study treatment to early permanent discontinuation of study due to AEs may be generated if there are a substantial number of such events.

Commented [XM25]: Please add sections:

- Multiple Comparisons/Multiplicity
- Patient Characteristics
- Prior Medication and Concomitant Therapy
- Protocol Violations

Commented [WWY26R25]: Refer to attached sample SAP

Commented [JAT27R26]: Added the new section 5.7.

